- a) Heart rate and blood pressure response
- b) Peripheral vascular resistance
- c) Sympathetic tone
- d) Urinary MHPG-sulfate excretion
- e) Intoxication

f) Beck Depression Inventory scores on the days following methamphetamine administration

We predict that reserpine will not alter the effects of methamphetamine on:

- a) Pulse pressure
- b) Cardiac conduction and repolarization
- c) Cardiac output
- d) Vagal tone
- e) Craving for methamphetamine

3. Background and Significance

A variety of pharmacological strategies are being pursued in the search for an effective treatment for methamphetamine addiction. One approach has been to target the dopaminergic neurotransmitter system involved in the reward mechanism to interrupt the reinforcing action of methamphetamine and thus reduce its use and prevent relapse (Hyman and Nestler 1996; [name] and Mello 1996; Ling and Shoptaw 1997). Methamphetamine is thought to produce its major effects through dopaminergic mechanisms in the midbrain. Methamphetamine causes dopamine release and blocks the reuptake of dopamine; the consequent excess of dopamine stimulates the midbrain reward centers. One therapeutic strategy is to develop and test dopamine antagonists to see if blocking dopamine can reduce methamphetamine abuse. A second, and diametrically opposed, therapeutic strategy is to develop and test dopamine agonists, agents that increase dopamine release or dopaminergic activity, to determine whether methamphetamine abuse can be reduced. This second strategy is based on a combination of theory and data suggesting that chronic methamphetamine use depletes brain dopamine and that this depletion is experienced as methamphetamine craving; the aim is to reduce methamphetamine craving and use by restoring the depleted dopamine system to normality.

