Chronic treatment with reserpine produces a different spectrum of effects than brief (single or only a few doses) treatment with reserpine. In contrast to the reversal of reserpine-induced hypolocomotion by d-amphetamine, rats chronically treated with reserpine are more sensitive to the acute stimulant effects of d-amphetamine. Although chronic reserpine-treated mice show an increased sensitivity to the toxic effects of amphetamine, no increase in lethality was seen (Stolk and Rech 1968). Chronic reserpine and amphetamine seem to produce similar effects with decreased self-stimulation responding in animal models (Leith and Barrett 1980).

Explicit mortality data was not presented in any of the studies described above. However, there were no comments suggesting an increased mortality in animals treated with reserpine and amphetamine (or cocaine).

4. Methods

a. Study Design

This 7-day double-blind, parallel-group, placebo-controlled inpatient study will compare the effects of 15 mg of intravenous methamphetamine given 60 hours before and 12 hours after a single oral dose of reserpine (0.5 or 1.0 mg) or placebo.

Subjects will be randomized to one of three parallel groups. A parallel group design (as opposed to a crossover design) is needed because the duration of action of even a single dose of reserpine is unpredictable. Reserpine irreversibly binds to the vesicular monoamine transporter; reversal of this effect requires synthesis of new transporter, a process that can take from one week to one month.

b. Methods of Data Analysis

As appropriate, statistical group comparisons will be made with PC-SAS's general linear model procedure (SAS Institute Inc., Release 6.04 Edition, Cary, NC, 1990) and with multifactor repeated-measures analysis of variance using SAS (UNIX) or SuperANOVA (Macintosh) software applications. Physiologic data will be transformed to change scores (post-treatment minus pre) and analyzed by repeated measures analysis of variance (ANOVA). After a significant F test, pairwise comparisons will be performed using the least squares means analysis. Effects will be considered statistically significant at P = 0.05.

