We have computed the power of our main measures from a prior methamphetamine study ([name] et al. 1995) similar to the study we propose. In this study, 30 mg of intravenous methamphetamine was administered and changes in heart rate $(20\pm17; mean\pm SD)$ were the smallest differences between active drug and placebo conditions. Based on Cohen's (1988) effect size formula, data from a study with a sample size of 6 would yield a power of 0.80. However, because the parallel group design increases between-subject variance, a larger n is needed. Therefore, correcting for the slightly small effect size, we estimate that a sample size of 10 per group will be sufficient to achieve a power of .80, using a two-tailed alpha = 0.05.

c. Subject Selection

1) Who and Why

Methamphetamine-experienced subjects between the ages of 21 and 45 years, in good physical and mental health, with no cardiovascular pathology will be accepted into the study.

2) Total Number — 30 Subjects

3) Inclusion/Exclusion Criteria

Inclusion Criteria

Subjects will be included in the study if they:

- 1) Are normotensive and between the ages of 21 to 45.
- 2) Are in good physical and mental health and have a body mass index between 18 and 30.
- 3) If female and have childbearing potential, are using an acceptable method of contraception and are not pregnant.
- 4) Are able to give voluntary informed consent.

Exclusion Criteria

Subjects will be excluded if:

- 1) They are currently dependent (using DSM–IV criteria) on alcohol or other psychoactive drugs (except nicotine and caffeine).
- 2) They have positive qualitative urine screens for drugs of abuse on admission the morning of dosing or during the screening examinations.
- 3) They have significant medical or psychiatric illnesses that might impair their ability to safely complete the study, that might be complicated by study medication, or that may interfere with absorption, distribution, metabolism or excretion of drugs.
- 4) They have a history of major depression or pharmacotherapy for depression or anxiety within the last year.

Subjects will not be allowed to take concomitant medications (other than birth control pills), whether prescription or over-the-counter (OTC); subjects needing regular doses of prescription medications will be excluded.

d. Subject Recruitment

1) Sources and 2) Initial Contact Method

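### Five predictions of no reserpine effect rest on a difference test at P = 0.05, which can refute them but cannot support them at 10 per group

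*Protocol*

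**What the plan says.** Protocol section 2 has two lists. The first predicts increases in, among others, heart rate and blood pressure response, sympathetic tone and intoxication. The second opens "We predict that reserpine will not alter the effects of methamphetamine on" and names pulse pressure, "Cardiac conduction and repolarization", cardiac output, vagal tone and craving. No margin or interval accompanies any of these five.

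Section 4.b turns physiologic data into change scores for repeated-measures ANOVA. Other group comparisons fall under a general sentence on linear models. It then says: "After a significant F test, pairwise comparisons will be performed using the least squares means analysis". The threshold is: "Effects will be considered statistically significant at P = 0.05". No other inferential rule is given.

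The sample size in section 4.b rests on heart rate changes of 20 (SD 17) in an earlier 30 mg methamphetamine study, chosen because they "were the smallest differences between active drug and placebo conditions". The text concludes that "a sample size of 10 per group will be sufficient to achieve a power of .80, using a two-tailed alpha = 0.05".

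**The concern.** A significance test is built to detect a difference. When the prediction is that there is none, the only result that agrees with it is P > 0.05, and a small trial produces that easily whether or not the prediction is true. Here the hypothesis and the rule, both fixed in the protocol, do not fit each other.

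This matters because section 3 gives, as one reason for the study, the need to show that reserpine can be used safely in people likely to take methamphetamine as well. QTc and cardiac output are on the no-effect list. An imprecise null on either could be taken as reassurance that the data do not give.

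**Working it through.** **Inputs.** Three groups of 10 (section 4.f); two-sided alpha 0.05, mean change 20 and SD 17 (section 4.b). Assumptions: one summary change score per subject, a common SD, and all 30 subjects contributing. The protocol gives no SD for any of the five no-effect outcomes, so results are in SD units.

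**1. The plan's own figure.** d = 20/17 = 1.18.
- The starting claim is that "data from a study with a sample size of 6 would yield a power of 0.80". The paired normal formula gives ((1.960 + 0.842)/1.176)² = 5.67, so 6. This reproduces.
- For two independent groups, 2 × 5.67 = 11.3, so 12 per group (13 with the t-test). At 10 per group the power is 0.75 (normal) or 0.70 (t). The stated 0.80 does not reproduce, and the step from 6 to 10 is not shown.
- More relevant here, the effect used is methamphetamine versus placebo. No reserpine-versus-placebo difference, and none of the five no-effect outcomes, was sized.

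**2. Precision of a dose-minus-placebo difference.** The half-width of the 95% interval is t(0.975, 27) × √(2/10) = 2.052 × 0.447 = 0.918 SD.
- An observed difference of zero leaves −0.92 to +0.92 SD open.
- A pairwise difference just short of significance leaves values up to about 0.92 + 0.92 = 1.84 SD open.
- For illustration only: with the heart rate SD of 17, 0.918 × 17 = 15.6 bpm.

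**3. How often a real difference goes unflagged.** One dose is shifted from placebo by the amount shown and the other is not. Shifting both doses gives the same values to within 0.01.

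| True shift (SD) | F test not significant | Pairwise test significant, after F gate | Pairwise test significant, no gate |
|---|---|---|---|
| 0.5 | 0.82 | 0.13 | 0.19 |
| 0.75 | 0.64 | 0.28 | 0.37 |
| 1.0 | 0.42 | 0.50 | 0.58 |
| 1.18 | 0.27 | 0.65 | 0.72 |

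If 0.5 mg has half the effect of 1.0 mg, gated power at 1.18 SD is 0.58. That is the least favourable of the three patterns tried.

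**4. What supporting 'no effect' would take.** The protocol states no margin, so a range is assumed. The method is two one-sided tests at 0.05 each, true difference zero, 80% power, n per group = 2((1.645 + 1.282)/margin)².

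| Margin (SD) | n per group needed | Power with 10 per group |
|---|---|---|
| 0.25 | 275 | about 0 |
| 0.5 | 69 | about 0 |
| 0.75 | 31 | 0.07 |
| 1.0 | 18 | 0.41 |
| 1.18 | 13 | 0.64 |

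These tests correspond to a 90% interval (half-width 0.76 SD). Requiring the 95% interval to lie inside the margin is stricter, so its power would be lower.

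**5. Predictions against measures.** The cardiovascular measures in section 4.f are vital signs, ECG with QTc, and impedance cardiography. None is named as an index of vagal or sympathetic tone, so those two predictions cannot be tested as written.

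**The case against.** The strongest reply is that the protocol never says what it will do with a null result, and that margins and intervals usually belong in a statistical analysis plan, which is not shown. The first half stands. A reader might infer that P > 0.05 will be declared to mean no interaction, or safety, but no sentence says so. Section 3 even treats a non-significant rise in mouse lethality as a reason to do this study, and gives exploring the interaction as a second purpose. The second half stands only in part: an analysis plan could supply a margin, but the protocol itself pairs no-effect hypotheses with a difference test.

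Four other tempting readings go too far.
- *Without a significant F the differences are not estimated.* Section 4.b makes pairwise comparisons conditional. It does not bar reporting group means or differences.
- *The F gate is itself an error.* It costs power (0.72 to between 0.58 and 0.65 at 1.18 SD), but with three groups it protects the familywise error rate. A fixed testing order for the doses would be a preference.
- *The bpm figure measures the problem.* Heart rate is a predicted increase, not one of the five, and its SD comes from a 30 mg study while this trial gives 15 mg.
- *Intoxication is unmeasured.* Section 4.f lists ratings of any drug effect and good drug effect, and section 1 adds adjective and visual analog scales. What is missing is a statement of which item stands for intoxication.

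**Conclusion.** The point holds as a mismatch between hypothesis and rule. For all five predictions the stated test can produce evidence against but none in favour, and with 10 per group a null result leaves differences of about 0.92 SD or more open. The half-width in SD units applies to any of the outcomes that is measured and reduced to one score per subject. Repeated measures, or use of the challenge given before reserpine, could change the precision, but the protocol gives no correlation from which to work this out. How large 0.92 SD is for QTc or cardiac output cannot be said from the document.

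Separately, vagal tone and sympathetic tone have no named measure. The documents do not support the claim that the sponsor has committed to reading non-significance as safety.

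**What to change.** In section 4.b:
- For the outcomes in section 2, report the 0.5 mg minus placebo and 1.0 mg minus placebo differences with 95% confidence intervals, whatever the F test shows.
- State that P > 0.05 will not be taken as evidence that an effect is not altered.
- For the five no-effect predictions, choose one of two routes. Either conclude 'not altered' only when the interval lies within a margin that is justified and fixed before unblinding, and otherwise state that no conclusion is possible; or label the predictions exploratory and report the estimates without a no-interaction conclusion. Given the power in step 4 of the working, the second route may be the more realistic.

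In sections 2 and 4.f:
- Name a measure for vagal and for sympathetic tone, derived from the ECG already recorded if the recordings allow, or withdraw those predictions.
- State which listed subjective item represents intoxication.

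The cost is wording, plus one justified margin per outcome if the first route is taken; no subjects are added. The downside is that most no-effect claims will be inconclusive at this sample size.

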Physiological Monitoring. On the days without methamphetamine challenges (days 0, 2, 3, and 5), subjects will have vital signs (heart rate, standing and supine blood pressure, respiratory rate, oxygen saturation, core temperature, and weight) and the noninvasive cardiac profile determined daily at 10 AM, 4 PM, and 8 PM. Vital signs will be obtained using a Critikon or Escort II monitor or a similar bedside device and noninvasive cardiovascular parameters measured using the instruments described above. On the days methamphetamine challenges are performed (study days 1 and 4), vital signs and the noninvasive cardiac profile will be obtained 15 minutes before and 5, 15, 30 and 60 minutes and at 1, 2, 3, 4, 6, 8 12, 18, 24, 30 36 and 48 hours after the infusion.

Subjective Measures. Subjective measures will be obtained daily at 8 AM, 4 PM, and 8 PM on study days 0, 2, 3 and 5. On days 1 and 4, when methamphetamine is administered, measures will be obtained starting 15 minutes before, and at 5, 15, 30, and 60 minutes, and 1, 2, 3, 4, 6, 8 12, 18, 24, 30 36, and 48 hours after the infusion. Items will include "any drug effect," "good drug effect," "bad drug effect," "headache," "dizziness," "desire for methamphetamine," and "craving for methamphetamine." The Beck Depression Inventory (Beck et al. 1996) will be administered daily at 4 PM.

Biosample Measures. All urine will be collected in 24-hour intervals and assayed for MHPG-sulfate by HPLC. On days 1, 4, and 6, aliquots will be sent for qualitative drugs of abuse screens.

Cardiovascular Measures. A series of non-invasive complementary cardiovascular measures assessing ventricular function (impedance cardiography), cardiac conductance and repolarization (ECG QTC interval), and peripheral vascular dynamics (impedance cardiography) will be obtained frequently throughout hospitalization. Data acquisition for the entire non-invasive panel requires about 10 minutes.

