Methamphetamine produces a sustained rise in systolic and diastolic blood pressure, most likely due to peripheral vasoconstriction. Peripheral vasoconstriction increases systemic vascular resistance (SVR). In the past, accurate measurement of SVR required right heart catheterization with attendant risks and complications. A new technique, Impedance Cardiography, allows accurate, rapid, and reproducible recording of several cardiovascular parameters, including SVR, noninvasively (Nelesen et al. 1999; Arthur and Kaye 2001). We will use impedance cardiography to measure the effects of methamphetamine-induced vasoconstriction on vascular resistance and cardiac work. Methamphetamine increases cardiac output, although the heart rate may be reflexively slowed ([name] et al. 1995). Subjects in this study are likely to experience some effect on left ventricular (LV) function after exposure to methamphetamine. Since clinical assessment cannot detect changes in LV function (Hardman et al. 1996), we will use impedance cardiography to measure LV function after methamphetamine.

Impedance cardiography will be measured using a computerized system consisting of a personal computer with customized data processing software, a transmitting unit with 4 pairs of electrodes for analyses of the thoracic impedance field. Two of these 4 electrodes will be placed above the sterno-cleidomastoid region of the subject's right and left neck; 2 more pairs will be placed in the midclavicular line on each side at the lower thoracic aperture at the xiphoid level.

Safety Criteria. Vital sign and behavioral abnormalities will be used to determine the safety of continued study participation. Vital signs must be within acceptable limits before reserpine (or placebo) is administered. Criteria for holding reserpine (or placebo) and terminating study participation are:

- 1. Supine heart rate >150 or <50, systolic blood pressure >180 or <95, diastolic blood pressure >120 or <50, respiratory rate >24 or <8.
- 2. Orthostatic systolic blood pressure change greater than 10 mmHg and/or heart rate change greater than 10 beats per minute.
- 3. Reported chest pain or dyspnea.
- 4. Subject confusion, agitation or inability to properly complete test procedures.
- 5. Any other significant adverse effect regarded as being due to the experimental procedures.

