If any of the following occur during or within 2 hours of methamphetamine dosing in the first challenge session, the subject will not continue in the study:

- 1. Supine heart rate > 80% predicted maximal for age or <50, systolic blood pressure >210 or <90, diastolic blood pressure >120 or <50, respiratory rate >24 or <8.
- 2. Significant arrhythmia defined as ≥6 beats nonsinus supraventricular tachycardia or =3 beats ventricular tachycardia.
- 3. Reported chest pain or dyspnea.
- 4. Subject confusion, agitation or inability to properly complete test procedures.
- 5. Any other adverse effect regarded as being due to methamphetamine or the experimental procedures.

If unexpected abnormal vital signs occur, subjects will be closely observed with vital sign measurements every 5 minutes until the abnormalities abate. If stopping criteria are exceeded, subjects will be closely observed for at least 24 hours before being discharged from the GCRC.

Alterations in CNS norepinephrine turnover produced by methamphetamine and reserpine will be assessed using urinary MHPG-sulfate excretion. Methamphetamine pharmacokinetic profiles will not be obtained because it is unlikely that alterations in the biodisposition of methamphetamine will be related to any pharmacodynamic effects. Reserpine pharmacokinetic profiles will not be obtained because venous levels are unrelated to pharmacologic effects. Subjective pharmacodynamic effects will be assessed with symptom reports and measured with visual analog scales.

Biological Samples

Urine Samples. All urine will be collected in 24-hour intervals (starting at 9:30 AM daily) and analyzed for MHPG-sulfate. A drug of abuse screen will be performed on admission and every 48 hours while on the GCRC and just before each methamphetamine dose.

2) Time (Frequency and duration of each study procedure; total amount of time)

Screening. The first visit to the laboratory will last 1 to 2 hours; subjects will complete routine screening questionnaires, undergo a 12-lead EKG, and provide blood and urine samples for routine labs. If subjects are called for a second visit, they will be compensated (see k below); this visit will involve a detailed history and physical exam by a physician and stress echocardiography, and will last approximately 2 to 3 hours.

Study Sessions. Subjects will be admitted to the UCSF General Clinical Research Center (GCRC) at Moffitt Hospital 24 hours before the first methamphetamine challenge. They will remain on

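### The repeated-measures ANOVA named in section 4.b can discard a whole subject for one missing reading, which costs precision in groups of 10 and leaves a conditional risk of bias

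*Protocol*

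**What the plan says.** **Analysis.** Section 4.b names the SAS general linear model procedure, together "with multifactor repeated-measures analysis of variance using SAS (UNIX) or SuperANOVA (Macintosh) software applications". For the physiologic outcomes it is specific: "Physiologic data will be transformed to change scores (post-treatment minus pre) and analyzed by repeated measures analysis of variance (ANOVA"). It does not say whether the multivariate or the univariate form is meant, which times enter, or what happens to an incomplete series.

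**Readings.** Section 4.f, Physiological Monitoring, schedules challenge-day vital signs and the cardiac profile at "15 minutes before and 5, 15, 30 and 60 minutes and at 1, 2, 3, 4, 6, 8 12, 18, 24, 30 36 and 48" (the second run of figures is in hours).

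**Exits.** Section 4.f, Safety Criteria, opens generally: "Vital sign and behavioral abnormalities will be used to determine the safety of continued study participation". Two lists follow.
- The first gives the criteria for holding reserpine or placebo and ending participation. It is introduced by a requirement on vital signs before that dose.
- The second applies to events "during or within 2 hours of methamphetamine dosing in the first challenge session, the subject will not continue in the study". Its limits run in both directions, for example "Supine heart rate > 80% predicted maximal for age or <50, systolic blood pressure >210 or <90".

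Both lists include "Subject confusion, agitation or inability to properly complete test procedures". After the second list comes a sentence with no time limit: "If stopping criteria are exceeded, subjects will be closely observed for at least 24 hours before being discharged from the GCRC".

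**Sample size.** Section 4.b takes a heart-rate change of 20 ± 17 from a study of 30 mg methamphetamine and sets 10 per group for power 0.80, two-tailed 0.05. It states no allowance for lost subjects.

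**The concern.** The trial asks whether reserpine increases the cardiovascular and behavioural response to methamphetamine before outpatients are exposed to both. The most informative data are the readings in the first hour or so after the second infusion. An analysis that needs every reading out to 48 hours can discard those acute data because a late reading was missed. With 10 per group, each such loss matters.

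There is a second, conditional issue. The exit criteria are built from heart rate, blood pressure and behaviour, which are the trial's outcomes or close to them. If they also end participation after reserpine, the subjects with incomplete series would be selected by their response. Complete-series analysis would then compare only those who tolerated the combination. In a study meant to detect additive toxicity, false reassurance is the costly error.

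**Working it through.** **1. The plan's own sample-size figures.** Inputs from section 4.b: difference 20, SD 17, two-sided 0.05, so d = 20/17 = 1.176.
- Starting figure of 6: one-sample normal formula, ((1.960 + 0.842)/1.176)² = 5.67, rounded up to 6. It reproduces.
- 10 per group, two-sample comparison: power is 0.75 by the normal formula and 0.70 by the noncentral t. The stated 0.80 is not reached even with complete data.

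**2. Readings per series.** Sixty minutes and 1 hour are the same time. The distinct post-infusion times are 5, 15, 30 and 60 min and 2, 3, 4, 6, 8, 12, 18, 24, 30, 36 and 48 h, which is 4 + 11 = 15. With the pre-infusion reading, a series has 16 readings per challenge, or 32 if both challenges enter. Reserpine is given at about 10 PM and the second infusion 12 h later, at about 10 AM, so the 18 h set falls at about 4 AM.

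**3. Cost of complete-series analysis.** Assume readings are missed independently at 1% or 2% each; the protocol gives no rate.

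| Readings needed | 1% missed | 2% missed |
|---|---|---|
| 16 | 0.99^16 = 0.85, or 8.5 of 10 | 0.98^16 = 0.72, or 7.2 of 10 |
| 32 | 0.99^32 = 0.72, or 7.2 of 10 | 0.98^32 = 0.52, or 5.2 of 10 |

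Two-sample t power at d = 1.176, by n per group:

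| n | 10 | 9 | 8 | 7 | 5 |
|---|---|---|---|---|---|
| Power | 0.70 | 0.65 | 0.59 | 0.53 | 0.37 |

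**4. Length of stay.** Section 4.f.2 has admission 24 h before the first challenge and discharge 48 h after the last. The challenges are 60 + 12 = 72 h apart. The total is 24 + 72 + 48 = 144 h, or six nights. The same section states five, and the payment ceiling in section 4.k also fits five: (30 + 5 × 150) × 1.10 = $858. Counting from a 10 AM admission, a fifth night ends 24 h after the second infusion. Discharge that day would miss the 48 h reading and, at 10 PM, the 36 h reading.

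**5. When could exits bias the interaction?** Simulation with assumed inputs: response 20 ± 17 at each challenge, true interaction 10, correlation between challenges 0.3 to 0.7. The strongest reactors are removed entirely, using a cut-off that takes the top 5, 10 or 20% of placebo subjects.

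| Exit depends on | Reserpine effect | Estimate (truth 10) | Retention |
|---|---|---|---|
| First challenge | Constant | 9.97 to 10.04 | Equal in both arms |
| First challenge | Proportional to reactivity | 9.1, 8.3 to 8.4, 7.0 (5, 10, 20% removed) | Equal in both arms |
| Second challenge | Constant | 6.5 to 9.2 | Unequal, e.g. 90% placebo, 76% reserpine |
| Second challenge | Proportional to reactivity | 5.5 to 7.7 | Unequal |

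The estimate is the between-group difference in change from the first to the second challenge. Only the second-challenge rows represent response-driven loss after reserpine.

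**6. Would the blood-pressure ceiling remove many subjects?** Suppose the first-challenge systolic limit of 210 also applied at the second challenge. Assume resting pressure 120, mean rise 20, SD 17 (a heart-rate SD at 30 mg, borrowed for want of another) and added reserpine effect 20. The reserpine mean is 160 and (210 − 160)/17 = 2.94 SD, so about 0.2% of that group is lost. The truncated-normal difference is 19.91, an understatement of about 0.4%. With resting pressure 130 it is about 2%.

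**The case against.** The strongest counter-argument is that the explicit exit rules act before reserpine can influence who leaves. One list covers only the first challenge, 60 h before reserpine; the other is tied to holding the reserpine dose. Under randomisation and blinding such exits cannot differ between arms because of reserpine, and no mixed model can recover a second challenge that never took place. This stands. A reader might infer that the planned analysis is biased toward no interaction; the documents do not support that as a flat statement.

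Several further points also stand, in whole or in part:
- Complete-series deletion is a default of one form of the procedure and is not written in the protocol. A univariate GLM with subject as a factor keeps partial series.
- Handling of missing data may sit in a statistical analysis plan that was not available. The point here is therefore about the method section 4.b does name, not about the absence of a missing-data section.
- The 24 h observation before discharge is a minimum, and section 4.f.2 keeps subjects until 48 h after the last dose. Loss of the 30, 36 and 48 h readings after a criterion is met is possible, not prescribed.
- The limits are two-sided. Section 3 describes reserpine as an antihypertensive. If it lowers pressure or rate in some subjects, exits at the low limits would remove low readings from the reserpine groups and raise their mean.

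A reader might also size the bias by applying the systolic limit of 180 to the second challenge. That limit governs holding reserpine, and step 6 shows that the challenge limit of 210 would remove almost nobody. Dyspnea is a more plausible trigger: it is an exit criterion, and section 4.g lists it among the most common effects of intravenous methamphetamine.

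**Conclusion.** The concern holds as a loss of precision, with a conditional risk of bias.

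- **Precision.** In its ordinary multi-time form, the named analysis loses a whole subject for one missing reading out of 16 per challenge. At the plan's own effect and SD, t-test power starts at about 0.70 and falls to 0.59 with 8 complete subjects per group and 0.53 with 7. This assumes the complete-case form is used and that 1 to 2% of readings are missed. The disputed length of stay could by itself make late readings missing for everyone.
- **Bias.** Differential loss that would bias the comparison between groups arises only if subjects are stopped or discharged early because of their response after reserpine. The two general sentences in Safety Criteria leave that open without establishing it. If it happened through upper limits, the simulated estimate was 5.5 to 9.2 of a true 10; those figures illustrate the mechanism and do not forecast this trial. Because the limits are two-sided, the direction is not certain.

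This is a cheap and worthwhile improvement to a stated method. It is not evidence that the trial's answer will be wrong.

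**What to change.** 1. In section 4.b, replace the repeated-measures ANOVA of change scores with a likelihood-based mixed model with group, time, group × time and the pre-infusion value. Use every available reading from every subject given reserpine or placebo, including those up to and at the moment a criterion is met.
2. Prespecify a parsimonious within-subject covariance. An unstructured matrix for 15 times has 15 × 16/2 = 120 parameters, too many to estimate reliably from 30 subjects.
3. State that no subject is dropped for an incomplete series.
4. Tabulate by group the subjects who meet a safety criterion after reserpine or placebo, since meeting one bears directly on the safety question.
5. Reconcile the Safety Criteria wording on whether the criteria apply after reserpine and at the second challenge, and whether readings continue once one is met. Reconcile the five-night stay with the six nights that the schedule implies. Which clinical rule or length of stay is right is for the investigators.

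**Cost.** Items 1 to 4 need wording and a little more analysis work, with no extra subjects or procedures. Item 5 is wording too, unless the stay is settled at six nights, which adds a ward night and its payment. The main downside is that the model rests on a covariance assumption that can be checked only roughly at this sample size. It also cannot supply second-challenge data for subjects who leave before reserpine.
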